### Guidelines for Preparing a Research Protocol

#### Instructions:

- You do not need to complete this document if you are submitting an *Application for Exemption* or *Application for a Chart Review*.
- Do not use this template if:
  - Your study involves an FDA regulated product. In this case, use the *Clinical Trial Protocol Template*.
  - Your study has a protocol from a sponsor or cooperative group. In this case, use the *Protocol Plus*.
  - Your study is a registry or repository for data and/or samples, In this case, use *Protocol Template – Registry Studies*.
- If a section of this protocol is not applicable, please indicate such.
- Do not delete any of the text contained within this document.
- Please make sure to keep an electronic copy of this document. You will need to use it, if you make modifications in the future.
- Start by entering study information into the table above, according to these rules:
  - Protocol Title: Include the full protocol title as listed on the application.
  - Investigator: include the principal investigator’s name as listed on the application form
  - Date Revised: Indicate the date at which the protocol was last revised
  - IRB Number: Indicate the assigned IRB number, when known. At initial submission, this row will be left blank.
- Once the table information in entered, proceed to page 2 and complete the rest of the form.

â Continue to next page to begin entering information about this study â

### 1. PREVIOUS STUDY HISTORY

Has this study ever been reviewed and rejected/disapproved by another IRB prior to submission to this IRB?

No  Yes - if yes, please explain:

## 2. BRIEF SUMMARY OF RESEARCH

- *The summary should be written in language intelligible to a moderately educated, non-scientific layperson.*
- *It should contain a clear statement of the rationale and hypothesis of your study, a concise description of the methodology, with an emphasis on what will happen to the subjects, and a discussion of the results.*
- *This section should be ½ page*

The purpose of this project is to identify the minimum effective dose (MED) of a multi-component behavioral change intervention required to increase levels of physical activity (PA) among participants on primary prevention statin therapy who are at elevated risk for cardiovascular disease (CVD). The long-term goal is to prevent CVD. The current project will utilize a modified version of the time- to- event continual reassessment method method (TiTE-CRM) [1,2] , a state-of-the-art dose finding methodology, to determine the MED of a multi-component behavioral change technique (BCT) intervention required to increase PA by an average of 2,000 steps per day. The intervention will be comprised of 5 BCTs which have previously shown to be effective on increasing health behaviors: Goal Setting, Action Planning, Self-Monitoring, Feedback, and Prompts/Cues [3-6].

The sample will include individuals prescribed primary prevention statin therapy with self-reported low levels of physical activity. Participants will complete a 2-week baseline run-in period where PA levels will be measured using Fitbit wearable devices and levels of adherence to statin medications will be assessed using eCAP smart pill bottles. During the baseline period, data from the Fitbit wearable devices will be used to verify participant's level of objective sedentary behavior. Individuals who are non-adherent to the protocol will be excluded and will not be randomized to the intervention. Following baseline, we will randomize 42 participants into 14 cohorts of 3 participants each for the intervention period. During the intervention period, participants will receive a BCT intervention, the length of which varies between 1 and 10 weeks depending on the assigned dose of a multi-BCT intervention. Assignment to doses will utilize modified TiTE-CRM methodology to adjust the dose for each cohort based on the results from the previous cohort. Following the intervention, all participants will be assessed over a 2-week follow-up period which includes passive data collection from the activity monitor, answering surveys and use of eCAP smart pill bottles to track medication adherence.

All collected data will be stored in the REDCap program, which is a Northwell IRB and Research IT security approved application, housed on the Northwell IT approved server. The MED will be defined as the smallest BCT dose duration associated with 80% of participants having a successful PA increase between the run-in and the follow-up periods. Change in PA will be defined as the difference in average daily PA between the run-in and follow-up periods. We will also assess Mechanisms of Action (MoAs) to determine potential mediators of the BCT intervention on PA. As increasing

PA may change statin adherence [7, 8], we will utilize eCAP smart pill bottles to measure adherence to statin medications.

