### 4. OBJECTIVE(S)/SPECIFIC AIMS AND HYPOTHESES

- *A concise statement of the goal(s) of the current study.*
- *The rationale for and specific objectives of the study.*
- *The goals and the hypothesis to be tested should be stated.*

The current study aims to identify the required dose of a behavioral change technique (BCT) intervention to increase physical activity (PA) by an average of 2,000 steps per day among individuals on primary prevention statin therapy with elevated risk for cardiovascular disease (CVD). The study will utilize the modified time-to-event continual reassessment method (TiTE-CRM).

**Primary Aim:** Identify the MED of a multi-BCT intervention required to increase PA by an average of 2,000 steps per day between run-in and follow-up periods in at least 80% of participants.

**Secondary Aim 1:** To identify effect sizes for mediating MoAs of the BCT intervention on PA.

**Secondary Aim 2:** Identify additional benefits of the BCT intervention on statin adherence.

**Exploratory Aim:** Identify between-person heterogeneity in Treatment Response.

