## 12. STATISTICAL ANALYSIS

- *Describe how your data will be used to test the hypotheses.*
- *State clearly what variables will be tested and what statistical tests will be used.*
- *Include sample size calculations.*
- *If this is a pilot study, state which variables will be examined for hypothesis generation in later studies.*

Analysis for the Primary Aim: The minimum effective dose (MED) will be defined as the smallest BCT dose duration associated with a successful PA increase (defined as an average increase of 2,000 steps per day) between the 2-week run-in and 2-week follow-up periods in at least 80% of participants. The MED will be estimated based on the modified TiTE-CRM, which is an adaptive model-based, dose-finding design for estimating the maximum tolerated dose in pharmacologic agents. In this study, we will adapt the TiTE-CRM for the purpose of MED estimation. Briefly, the TiTE-CRM operates as follows during a study. Participants will be enrolled in cohorts of 3. The first cohort will be given a BCT intervention with a duration of 5 weeks. Subsequent cohorts will be given a BCT intervention duration (from 1-week to 10-week) based on the updated MED estimate according to the modified TiTE-CRM model and data from the previously enrolled participants. The process will continue until we reach a total of 42 participants (14 cohorts) randomized to the intervention. Once the study has completed enrollment, we will identify which dose of the BCT intervention (in weeks) is associated with  $\geq 80\%$  of participants achieving the goal of an average of 2,000 steps per day increase between the baseline and follow-up periods. Means and standard deviations of step scores for baseline versus behavioral change strategy treatment period will be visualized using a column graph. The statistical significance of differences will be adjusted for time interval. The effects of treatment on number of steps will be assessed using generalized linear mixed models (GLMM). This model will account for possible autocorrelation and linear trends between steps across time.

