The dose-efficacy model is calibrated such as that the modified TiTE-CRM will eventually select a BCT duration associated with 75%-85% successful PA success, i.e., within 5 percentage points of our target [30]. The sample size (n=42) is determined to achieve 60% probability of correct selection (PCS) under logistic dose-efficacy curves with slope = 0.69 (i.e., an OR = 2) [31]. As this is small-scale pilot study, power and sample size will be calculated solely for the primary aim.

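### The primary result is one named duration with an at-least-80% success claim, and no interval, posterior probability or set of compatible durations is planned for it

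*Combined protocol and SAP*

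**What the plan says.** Section 2 (Brief Summary of Research) gives the definition: "The MED will be defined as the smallest BCT dose duration associated with 80% of participants having a successful PA increase". The Primary Aim in Section 4 asks for the required step increase "between run-in and follow-up periods in at least 80% of participants". Section 12 (Statistical Analysis) describes the last step of the primary analysis this way: "Once the study has completed enrollment, we will identify which dose of the BCT intervention (in weeks) is associated with" success in 80% or more of participants.

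The sample-size text in Section 12 gives the only precision figure, "60% probability of correct selection (PCS) under logistic dose-efficacy curves" with slope 0.69 (odds ratio 2) and 42 participants. It also says the design is calibrated so that it will eventually "select a BCT duration associated with 75%-85% successful PA success, i.e., within 5 percentage points of our target".

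Two other statements in Section 12 might seem to cover uncertainty but do not. The generalized linear mixed model concerns step counts, not the MED. The promise of transparent reporting is made so that differences between individuals can be judged.

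**The concern.** A PCS describes how the design behaves before any data exist. It says nothing about how firmly the data obtained support the chosen duration. Followed exactly, the plan produces a number of weeks and the statement that at least 80% of participants succeed at it. A reader could not tell whether a success rate in the high 60s is excluded, or whether the weeks on either side would do as well.

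The final rule is also unclear. Sections 4 and 12 (and the word smallest in Section 2) suggest choosing the smallest duration that reaches 80%. The 75% to 85% calibration in Section 12 suggests choosing the duration closest to 80%, and so tolerates a true rate below 80%. The strength of the closing claim depends on which of these applies.

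**Working it through.** **Inputs from the plan.** 42 participants in 14 cohorts of 3, first cohort at 5 weeks, durations from 1 to 10 weeks (Sections 9 and 12); target 80%, tolerance 75% to 85%, logistic slope 0.69, PCS 60% (Section 12).

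**Assumed, because the documents do not say.** The slope is per week, durations move in weekly steps, and outcomes are complete before each assignment. The working model and prior are also assumed, as stated below.

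**1. The curve.** Put the 80% point on a whole week m: logit p(w) = ln 4 + 0.69 × (w − m), with ln 4 = 1.386.
- One week shorter: 1.386 − 0.69 = 0.696, so p = 66.7%.
- One week longer: 1.386 + 0.69 = 2.076, so p = 88.9%.

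If the 80% point lies midway between two weeks, the shift is 0.345 each way. The logits are 1.041 and 1.731, giving 73.9% and 85.0%.

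**2. Reproducing the 60%.** A one-parameter power-model CRM (half-width 0.05, normal prior variance 1.34, prior MED at week 5 or 6, 3,000 trials per scenario, closest-to-target selection) gives mean PCS of 0.595 to 0.602 for a true MED at weeks 2 to 9. The plan's figure is reproduced.

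In those runs about 60% of trials name the right week, about 27% a week that is too long and about 13% one that is too short. A duration that is too long is the wrong MED but still gives at least 80% success. So the at-least-80% statement is true in about 60% + 27% = 87% of these trials.

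**3. What the final data would show.** A one-parameter logistic CRM (slope fixed at ln 2 per week, prior SD 2 on the intercept, closest-to-80% allocation) gives PCS of 57% to 64% with the 80% point on week 3, 5 or 7, so it is also in line with the plan. About 18 to 24 participants end on the selected duration, and the 95% credible set for the MED holds about 3 durations. The rest depends on the final rule:

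| Quantity at the selected duration | Closest to 80% | Smallest with estimate ≥ 80% |
|---|---|---|
| 95% credible interval for success | about 67%–91% | about 73%–93% |
| Mean posterior Pr(success ≥ 80%) | about 0.58–0.59 | about 0.81 |
| True success ≥ 80%, 80% point on a whole week | about 84%–88% of trials | about 97% |
| True success ≥ 80%, 80% point between weeks | about 55%–64% of trials | about 79%–87% |

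**4. A check that uses no dose-response model.** With 17 successes in 21 participants (81%), the exact 95% interval is 58% to 95%. Even if all 42 were treated at one duration, 34/42 (81%) gives 66% to 91%.

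**The case against.** The plan is candid about its scale. It calls the study a pilot, says the MED will be estimated, aims only for a preliminary assessment, and states both the 60% PCS and the 5-point tolerance. Nothing in it forbids reporting intervals, and every simulated figure above rests on a working model and prior that the documents do not give. All of this is correct. It makes the figures illustrative and makes this a reporting matter rather than a design fault. It does not supply the missing output, because a pilot's estimate is of little use without its uncertainty.

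A reader might go further and infer from the 60% PCS that, on the plan's own assumptions, the at-least-80% claim is barely better than a coin toss. The documents do not support that. The 60% is the chance of picking exactly the right week among ten, where a random pick would be right 10% of the time. In the setting that reproduces it, with some week at exactly 80%, the claim is true in about 84% to 88% of trials. It falls to about 55% to 64% only if two conditions hold together: the 80% point lies between weeks, and the final pick is the duration closest to 80%. The plan fixes neither.

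It would also be speculation to say that a later study will adopt the chosen duration as settled; the documents describe no such study.

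**Conclusion.** The omission is real and should be corrected. The primary analysis yields a single duration and an at-least-80% statement, with nothing to show how well the data support either. On illustrative assumptions the 95% credible interval spans about 20 to 24 percentage points (73% to 93%, or 67% to 91%), and about three durations remain compatible with the data. The 60% PCS cannot stand in for this, because it answers a different question.

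How often the closing claim would be true runs from about 55% to about 97%, depending on the final selection rule and on where the 80% point falls relative to whole weeks. The first of these is the plan's to state, and it does not state it clearly: accepting 75% to 85% does not match at least 80% in Sections 4 and 12. An unknown slope or incomplete outcomes would be expected to widen the intervals.

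**What to change.** Amend the primary analysis in Section 12 as follows.

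- From the final model fit, report for every duration the posterior mean success with a 95% credible interval, Pr(success ≥ 80%), Pr(this duration is the MED), and the numbers treated and successful.
- State which final selection rule applies, closest to 80% or smallest with an estimate of at least 80%, and reconcile it with the 75% to 85% calibration and with the definitions in Sections 2 and 4.
- Word the conclusion as: estimated MED X weeks (95% credible set …), success p% (95% credible interval …), in place of an unqualified at-least-80% statement.

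A fitted Bayesian CRM already contains these quantities, so no participants are added and allocation does not change. The cost is a little more analysis work and a less definite headline.

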### 3. INTRODUCTION/BACKGROUND MATERIAL/PRELIMINARY STUDIES AND SIGNIFICANCE

- *Describe and provide the results of previous work by yourself or others, including animal studies, laboratory studies, pilot studies, pre-clinical and/or clinical studies involving the compound or device to be studied.*
- *Include information as to why you are conducting the study and how the study differs from what has been previously researched, including what the knowledge gaps are.*
- *Describe the importance of the knowledge expected to result*

Cardiovascular disease (CVD) remains the leading cause of mortality [9] and morbidity [10] in the United States. Statin therapy is a mainstay of CVD prevention, with multiple, large randomized controlled trials (RCTs) demonstrating that statin therapy decreases the probability of CVD events [11-13]. However, research has shown that statin therapy alone is insufficient for preventing incident CVD and mortality [8-11][14-16].

Walking an additional 2,000 steps per day has been found to have a clinically significant impact on CVD risk [16]. Combining statin medication with physical activity (PA) can lower mortality risk more than either statin or PA alone [14,15]. Further, the addition of PA to statin therapy can have additional benefits, such as increased cognitive functioning [17] and reduced side effects for statin therapy [18,19]. Despite the importance of increasing PA while on statins, PA levels often remain the same following statin prescription [20] and may even decline [21].

Multi-component behavioral change technique (BCT) interventions have demonstrated modest efficacy for increasing PA [22-24] and medication adherence [3,25]. However, no research has examined the dose of a multi-BCT intervention required to produce a clinically meaningful increase in PA. By using a modified version of the time-to-event continual reassessment method (TiTE-CRM), the current study can identify the required dose of a BCT intervention to increase PA by an average of 2,000 steps per day among individuals on primary prevention statin therapy at elevated risk for CVD.

### 4. OBJECTIVE(S)/SPECIFIC AIMS AND HYPOTHESES

- *A concise statement of the goal(s) of the current study.*
- *The rationale for and specific objectives of the study.*
- *The goals and the hypothesis to be tested should be stated.*

The current study aims to identify the required dose of a behavioral change technique (BCT) intervention to increase physical activity (PA) by an average of 2,000 steps per day among individuals on primary prevention statin therapy with elevated risk for cardiovascular disease (CVD). The study will utilize the modified time-to-event continual reassessment method (TiTE-CRM).

**Primary Aim:** Identify the MED of a multi-BCT intervention required to increase PA by an average of 2,000 steps per day between run-in and follow-up periods in at least 80% of participants.

**Secondary Aim 1:** To identify effect sizes for mediating MoAs of the BCT intervention on PA.

**Secondary Aim 2:** Identify additional benefits of the BCT intervention on statin adherence.

**Exploratory Aim:** Identify between-person heterogeneity in Treatment Response.

## 5. RESOURCES AVAILABLE TO CONDUCT THE HUMAN RESEARCH

- *Explain the feasibility of meeting recruitment goals of this project and demonstrate a potential for recruiting the required number of suitable subjects within the agreed recruitment period*
  - *How many potential subjects do you have access to?*
- *Describe your process to ensure that all persons assisting with the trial are adequately informed about the protocol and their trial related duties and functions*

Northwell Health employs over 77,000 individuals. Inter-departmental support has been shown across Northwell to assist the researchers in meeting recruitment goals. Their extensive electronic communication system will allow for the rapid delivery of recruitment materials directly to potentially-eligible participants. Virtual electronic screening and consent processes, employment of participant smart phones for protocol reminders and notifications, and integration with existing Northwell Health policies will minimize burden to participate for those who are interested in the study.

Center for Personalized Health staff must meet certain eligibility criteria before assisting with this study. All staff members must be listed on the IRB and be up-to-date with trainings and attestations as required by the Northwell Health Human Research Protection Program. Additionally, staff will be required to participate in weekly meetings with the Principal Investigator and an additional weekly meeting with the Project Manager, in order to stay informed about the study protocol, staff duties and functions, and to answer any questions that come up within the group. Staff will have daily access to the Project Manager, Director of Clinical Research, and Principal Investigator to answer any protocol questions they may have outside these established weekly meetings.

## 6. RECRUITMENT METHODS

- *Describe the source of potential subjects*
- *Describe the methods that will be used to identify potential subjects*
- *Describe any materials that will be used to recruit subjects. A copy of any advertisements (flyers, radio scripts, etc.) should be submitted along with the protocol.*
- *If monetary compensation is to be offered, this should be indicated in the protocol*

The study will be advertised to potential participants (those taking statin medication) via established Northwell communication channels, including email. This extensive electronic communication system allows for the rapid delivery of recruitment materials directly to potentially eligible participants including, but not

limited to, advertisement on TV monitors in office locations in collaboration with Northwell Marketing.

For additional recruitment, we will utilize the Quantitative Intelligence (QI) group to identify potential participants via history of statin medication prescription (to meet inclusion criteria) and **diagnostic codes for cardiovascular disease and severe mental illness, via** Touchworks. Potential participant's phone number and emails will also be collected. Once identified, eligible participants will be called directly and/or sent an email that provides a link to review the consent document if they are interested in participating or contact study personnel if they have questions. In situations where an individual is upset they have been contacted and/or the study team has their information for that purpose, we will clarify that no one on the study team has reviewed their records, but that we respect their privacy and they will not be contacted for this study again.

Recruitment links will lead to a study web page with more information about study requirements, eligibility, and who to contact for more information. There is no payment to subjects for participation in this research, however participants will be allowed to keep their commercially available Fitbit device at the end of the study. Participants will be required to return their eCAP smart pill bottle at the end of the research study.

## 7. ELIGIBILITY CRITERIA

- *Describe the characteristics of the subject population, including their anticipated number, age, ranges, sex, ethnic background, and health status. Identify the criteria for inclusion or exclusion of any subpopulation.*
- *Explain the rationale for the involvement of special classes of subjects, such as fetuses, pregnant women, children, prisoners or other institutionalized individuals, or others who are likely to be vulnerable. You cannot include these populations in your research, unless you indicate such in the protocol*
- *Similarly, detail exclusionary criteria: age limits, special populations (minors, pregnant women, decisionally impaired), use of concomitant medications, subjects with other diseases, severity of illness, etc.*

